## 1 Protocol Summary

Study Title	Prostatic Urethral Lift in Subjects with Acute Urinary Retention Study (PULSAR)
Study Objectives	Assess feasibility and safety of the Prostatic Urethra Lift (PUL) procedure in patients with acute urinary retention secondary to BPH. Research methodology will also be evaluated for larger, randomised study.
Study Design	Multi-centre, prospective evaluation of PUL and retrospective review of invasive surgery as potential comparator.
Sample Size	Up to 55 subjects treated with PUL. Retrospective chart review will include BPH patients that presented with AR and went on to de novo invasive surgery from June 1, 2015 to December 31, 2015.
Subject Population	Males over the age of 50 diagnosed with symptomatic benign prostatic hyperplasia (BPH) and ongoing acute urinary retention after failed TWOC.
Number of Centres (Sites)	Up to six centres in the United Kingdom.
Clinical Indication	The UroLift System is indicated for the treatment of symptoms due to urinary outflow obstruction secondary to benign prostatic hyperplasia (BPH) in men 50 years of age or older.
Primary Study Assessment	Successful post-procedure voiding trial without catheter (2-4 days).
Safety Assessment	Rate of serious adverse events (SAEs) related to BPH intervention through 3 months.
Additional Assessments	1. Need for further clean intermittent self-catheterisation (CISC) 2. Urinary symptoms, post void residual (PVR) and peak flow rate over follow-up 3. Subjects free from urinary retention through 1 month, 6 weeks, 3, 6 and 12 months 4. Subjects free from alternative surgical procedure for BPH through 12 months 5. Duration of catheter prior to treatment and in follow-up between prospective (PUL) and retrospective (TURP/HoLEP) 6. Rate of AEs in prospective PUL and retrospective TURP/HoLEP 7. Assess enrolment rate, willingness of patients to enrol, inclusion criteria, and appropriateness of endpoint
Follow-up Evaluations	Post-procedure, 6 weeks, 3 months, 6 months (remote), 12 months
Anticipated Study Duration	
First patient in (FPI)	15-April-2018
Last patient in (LPI)	31-December-2018
Endpoint analysis	28-February-2019
Study close	01-April-2020

### 3 Abbreviations and Definitions

**Table 1 Abbreviations**

AE	Adverse Event
AIDS	Acquired Immunodeficiency Syndrome
AR	Acute urinary retention
AUR	Acute urinary retention
BPH	Benign Prostate Hyperplasia
BPH II	Benign Prostatic Hyperplasia Impact Index
CAPA	Corrective and Preventative Action
CEC	Clinical Events Committee
CI	Confidence Interval
CIP	Clinical Investigation Plan – Study Protocol
eCRF	Electronic Case Report Form
CT	Capsular Tab
DRE	Digital Rectal Exam
EC	Ethics Committee
EDC	Electronic Data Capture (system)
FDA	Food and Drug Administration
GDPR	General Data Protection Regulation
GCP	Good Clinical Practices
GU	Genitourinary
HoLEP	Holmium Laser Enucleation of the prostate, alternative to TURP
HRA	Health Research Authority
HREC	Human Research Ethics Committee
IB	Investigator's Brochure
ICF	Informed Consent Form
ICH	International Conference on Harmonisation
IDE	Investigational Device Exemption
IFU	Instructions for Use
IIEF	International Index of Erectile Function
IPSS	International Prostate Symptom Score
IR	Independent Reviewer
ISI	Incontinence Severity Index
ITT	Intention-to-Treat
L.I.F.T.	Luminal Improvement Following Prostatic Tissue Approximation for the Treatment of Lower Urinary Tract Symptoms
LUTS	Lower Urinary Tract Symptom
MHRA	Medicines and Healthcare Products Regulatory Agency

MI	Multiple Imputation
MIST	Minimally Invasive Surgical Therapies
OUS	Outside U.S.
PET	Polyethylene Terephthalate
PP	Per Protocol
PRN	As needed
PSA	Prostate-Specific Antigen
PUL	Prostatic UroLift Procedure- procedure using the UroLift System
PVP	Photoselective vaporisation of the prostate by laser, alternative to TURP
PVR	Post Void Residual
Qmax	Peak Flow Rate
QoL	Quality of Life
R&D	Research & Development
Rx	Prescription Only
SAE	Serious Adverse Event
SAP	Statistical Analysis Plan
SOC	Standard of Care
SHIM	Sexual Health Inventory for Men
TBD	To Be Determined
TRUS	Transrectal Ultrasound
TWOC	Trial to void without catheter
TURP	Transurethral Resection of the Prostate
UA	Urinalysis
U.S.	United States
US	Ultrasound
VAS	Visual Analog Scale

**Table 2 Definitions**

Adverse event (AE)	An adverse event (AE) is defined as any undesirable medical occurrence in a clinical trial subject, whether it is considered to be related to the device or not, that includes a clinical sign, symptom, or condition.  Once a subject is enroled, all AEs must be reported through follow-up period. Only exacerbated conditions or new onset qualify as an AE. Principal Investigator will assess severity, relatedness, serious or unexpected.
Alternative Surgical Intervention	A post-index procedure surgery, other than PUL, to treat BPH.
Acute Urinary Retention	Painful inability to void and a residual volume < 1500 mL.
Invasive BPH surgery	
 
• Transurethral resection of the prostate (TURP)
 
• Transurethral Laser (PVP, HoLEP or Interstitial)
 
• Open Prostatectomy
 

Index procedure	The first procedure to which subjects are enroled.
Precipitated AR	Acute urinary retention that develops in response to a trigger such as UTI, anaesthesia, surgery, medications with sympathomimetic or anticholinergic effects.
Serious Adverse Event (SAE)	
Serious Adverse Event (SAE) is defined as untoward occurrence that: (a) results in death; (b) is life-threatening; (c) requires hospitalisation or prolongation of existing hospitalisation (d) results in persistent or significant disability or incapacity; (e) consists of a congenital anomaly or birth defect; or (f) is otherwise considered medically significant by the investigator.
 
(in-patient hospitalisation is at least 24 consecutive hours)

Unexpected Adverse Event	An unexpected adverse event is an event which by nature, incidence, severity or outcome has not been identified in the current version of the Sponsor risk management files.
Spontaneous AR	Associated with older age, BPH, elevated PSA, or presence of severe LUTS.
PUL Procedure Time	Time from first device insertion to last device removed.

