**Table 4 L.I.F.T. Procedure Information**

Procedure Component		UroLift (N = 140)	Control (N = 66)
		% (n/n responses)	
Anaesthesia	Topical / Lidocaine jelly	90.7 (127/140)	90.9 (60/66)
	Prostate block	1.4 (2/140)	3.0 (2/66)
	Spinal	0 (0/140)	0 (0/66)
	General	17.9 (25/140)	16.7 (11/66)
Prophylactic Antibiotics Used		100 (140/140)	100 (66/66)
Sedation	Oral	67.9 (95/140)	68.2 (45/66)
	Intramuscular	0.7 (1/140)	0 (0/66)
	Intravenous	30.0 (42/140)	33.3 (22/66)
Catheter Placed Prior to Discharge		39.3 (55/140)	10.6 (7/66)
Mean, Median, SD [min - max], (n)			
Cystoscopic Intervention Time  (min)		24.4, 21.0, 12.45 [5 - 65], (140)	9.6, 8.0, 5.54 [2 - 25], (65) 
UroLift Procedure Time  (min)		18.7, 15.0, 11.07 [3 - 57], (140)	
Overall Procedure Time  (min)		66.2, 63.0, 23.84 [24 - 162], (140)	46.8, 45.0, 17.21 [18 - 100], (65) 
Time to Return to Pre-operative Activity Level (days)		8.6, 7.0, 7.53 [0 - 43], (140)	3.1, 2.0, 4.38 [0 - 28], (66)

Procedure Component	UroLift (N = 140)	Control (N = 66)		
	% (n/n responses)			
 Defined as cystoscopic start time to procedure end time.				
 Defined as time from 1st device insertion to last device removal.				
 Defined as start of anaesthesia time to time subject leave procedure room.				
 Subject 218-001 did not have a procedure end time recorded, thus only 65 cystoscopic intervention times and overall procedure times are available.				
Source: de novo one year report				

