### 10.3.4 Post Procedure Instructions

After creating an unobstructed anterior channel, continue with cystoscopy to verify implants are not present in the bladder, or extending into the bladder vesical. Interrogate the bladder neck for protruding implants. If a protruding or exposed implant is present, it should be removed.

A urinary catheter will be placed prophylactically after the Investigator completes the UroLift procedure, and subject provided instructions on its proper maintenance. The subject should remain on

alpha blockers per the site's standard of care. Initiation and cessation should be documented on the concomitant medication log. A post-procedure follow-up visit to perform Trial without Catheter will be scheduled for 3 days ( $\pm 1$  day) after index procedure.

The Investigator or designee will record the following procedural data:

- Device: number of UroLift devices used, location of implantation, lot number, performance
- Cystoscopy findings, including confirmation of inclusion criteria, stones, and other notable pathology
- Time: subject enters and leaves procedure room, first/last UroLift device, catheter placement
- Anaesthesia/sedation: duration, type, and delivery of procedural medications
- Clinical staff required during the procedure
- Complications/adverse events
- Venue type (clinic, outpatient, inpatient, etc.)
- Time to discharge or release from treatment facility
- Urinary catheter placement, type and timing (length)
- Medications used
- Post-operative interventions (if any)

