### 15.8.2 Procedure

The following will be collected (if available):

• Date, duration	• Type of facility, type of surgery	• Complications, adverse events (urological, sexual function, cancer and SAEs)	• Duration of hospital stay
• Catheterisation	• Pathology (documentation only)		

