### **Retrospective Arm**

The following baseline and procedural data points will be summarised for both the retrospective and the prospective arms. Although the study is not powered to make comparisons between the retrospective surgical patients and the prospective Urolift subjects, comparisons in the observed data will be made statistically. Continuous variables will be compared using a t-test or non-parametric alternative, binary data points will be compared using chi-square or Fisher's exact test.

- 1) Baseline demographics

- 2) Duration of catheterisation to procedure (days)
- 3) Procedure time
- 4) Hospitalisation time

The following outcomes post procedure will be summarised for the retrospective surgical group and will compared to the results obtained in the prospective study. The statistical significance of any observed differences will be assessed.

- 1) Total numbers of related AE, SAE, and Clavien-Dindo  $\geq$ IIb individually
- 2) Percent procedure/device related AE rates by month post index procedure and by severity
- 3) Retreatment post index intervention by time to event and by month
- 4) Medical treatment post index intervention by time to event and by month
- 5) Urinary retention recurrence rates at 1 month, 6 weeks and at 3, 6 and 12 months
- 6) Post-procedure TWOC success percent
- 7) Catheterisation use

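### Procedure time is to be tested between arms without a common clock: the only definition is device-specific and narrow, and the surgical duration has no stated start or stop

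*Combined protocol and SAP*

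**What the plan says.** Section 3, Table 2 defines PUL procedure time as "Time from first device insertion to last device removed". No other definition of procedure time is given for this study.

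Section 10.3.4 has the site record more time points than that definition uses: "Time: subject enters and leaves procedure room, first/last UroLift device, catheter placement".

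For the surgical patients, the time item in section 15.8.2 reads "Date, duration". It is collected only where the chart has it, and no start or stop point is given.

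Section 16.6, Retrospective Arm, lists "3) Procedure time" among the baseline and procedural items summarised for both arms. On testing it says: "Continuous variables will be compared using a t-test or non-parametric alternative". It also concedes the limits of the comparison: "Although the study is not powered to make comparisons between the retrospective surgical patients and the prospective Urolift subjects".

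Table 4, from the earlier L.I.F.T. trial, reports three different clocks for the same UroLift patients. The footnote to the narrowest reads "Defined as time from 1st device insertion to last device removal", which is in substance the Table 2 definition.

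**The concern.** A clock that starts with the first device and stops with the last has no counterpart in a TURP or HoLEP. It excludes anaesthesia, the cystoscopy before the first device, the check cystoscopy afterwards and catheter placement. A surgical chart may or may not exclude the equivalent steps, and the plan does not say. If the two arms are timed over different intervals, the test in 16.6 measures a mixture of the real difference and the difference in definition, and nothing in the output would separate them.

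Short operative time is one of the advantages put forward for PUL in section 6, and section 13.1 names a possible decrease in procedure time against other surgery. Item 3 in 16.6 is the one planned comparison that bears on this, and the study is meant to inform a larger trial.

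**Working it through.** The plan states no sample size, alpha or expected difference for this comparison, so it has no figure of its own to reproduce. The check uses Table 4 to see how much the choice of clock moves the result.

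**Inputs from Table 4 (UroLift arm, n = 140, minutes)**
- First device in to last device out: mean 18.7, median 15.0, SD 11.07.
- Cystoscope start to procedure end: mean 24.4, median 21.0, SD 12.45.
- Anaesthesia start to leaving the room: mean 66.2, median 63.0, SD 23.84.

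**Shift due to the clock alone**
- Cystoscope clock: 24.4 − 18.7 = 5.7 min; 24.4 / 18.7 = 1.30. Medians: 21 − 15 = 6 min.
- Room clock: 66.2 − 18.7 = 47.5 min; 66.2 / 18.7 = 3.54. Medians: 63 − 15 = 48 min.

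The medians move in the same way, so choosing the non-parametric test would not remove the problem.

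**What this does to the test**

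Assume that surgery truly takes as long as PUL, that PUL is timed on the Table 2 clock, and that surgery is timed on a wider one. Take 55 PUL men (the stated maximum), two-sided alpha 0.05 (assumed) and n surgical men (assumed, since the protocol gives no number).

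Expected t = gap / √(11.07²/55 + SD²/n)

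Rejection rate ≈ Φ(t − 1.96) + Φ(−t − 1.96)

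Example, cystoscope clock, n = 55: √(122.54/55 + 155.00/55) = √(2.23 + 2.82) = 2.25, so t = 5.7 / 2.25 = 2.54 and the rejection rate is Φ(0.58) ≈ 72%.

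| Surgical n | Cystoscope clock: t | Rejection, formula | Rejection, simulation | Room clock: rejection |
|---|---|---|---|---|
| 10 | 1.35 | 27% | 17% | about 100% |
| 20 | 1.80 | 44% | 41% | about 100% |
| 30 | 2.10 | 55% | 56% | about 100% |
| 55 | 2.54 | 72% | 72% | about 100% |

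The simulation column is a Welch test on lognormal times, 4,000 runs per cell. With the room clock, t is 8.6, 10.3 and 13.4 at n = 20, 30 and 55. With the same clock in both arms, the rejection rate returns to 5% by formula and 4 to 7% in simulation.

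**Which clock does 16.6 use?**

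Item 3 says only procedure time. It neither uses the Table 2 term nor refers to it. There are two readings:
- Table 2 governs. PUL then has a narrow clock and surgery an undefined one.
- Table 2 does not govern. The variable is then undefined in both arms, and the interval could be chosen after the data are seen.

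Both readings need the same repair. The document itself already uses the term in more than one sense: the L.I.F.T. text in section 5.1.1 gives a median procedure time of 63.0 min, measured from subject preparation to leaving the room. Table 4 gives no control value for the device clock; the two arms appear side by side only on the two clocks that they share.

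**The case against.** The strongest reply is that no bias is established. Section 16.6 does not commit to the narrow PUL clock, 10.3.4 records the room times as well, and the charts may hold an equally narrow instrument interval. That stands. A reader might infer that PUL will look shorter by definition alone, or that the comparison must always favour PUL. The documents support neither: no section says what a surgical chart's duration covers, and with matching narrow intervals the built-in gap is zero. Nor would the test be sure to reject. On the cystoscope clock it rejects in about half of trials or fewer unless the surgical arm is fairly large.

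The L.I.F.T. gaps may also not carry over. Those procedures were mostly done under topical anaesthesia, and here the planning cystoscopy may already have been done at screening (section 10.3.1). That stands too: the figures show that the clock matters, and do not forecast the gap in this study.

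Table 12 promises that the EDC and worksheets will guide abstractors, and that variables are used for consistency between the arms. These statements are general and none sets a time interval. The forms themselves are not available, so they might define one. Even so, the analysis section would still need to name the interval compared.

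Finally, the comparison is declared unpowered, and section 16.7 sets no success criteria. This limits the consequence but does not cure the problem. Low power is no protection against a systematic difference in measurement, which becomes more significant as the arms grow.

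**Conclusion.** The point holds as a conditional one. The plan tests procedure time between arms with a device-specific definition on one side and no definition on the other. If Table 2 governs and the charts use a wider clock, definition alone can contribute 5.7 min (1.30-fold) to 47.5 min (3.54-fold) on the L.I.F.T. figures. If the charts hold an equally narrow interval, it contributes nothing.

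The rejection rates rest on assumptions: equal true times, L.I.F.T. means and SDs standing in for both arms, two-sided alpha 0.05, and 10 to 55 surgical men. The documents give no TURP or HoLEP time.

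The effect is confined to one additional comparison. The primary TWOC assessment and the SAE assessment are not affected. The change is worth making because it is cheap and because a significant difference could not otherwise be interpreted.

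**What to change.** In 16.6, Retrospective Arm, item 3, state that only matching intervals are compared: PUL room entry to room exit, already recorded under 10.3.4, against theatre-in to theatre-out abstracted under 15.8.2.

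- Have the abstractor record which start and stop each chart gives. Leave charts without the matching interval out of this comparison and report how many there are.
- Flag PUL cases in which screening tests were done in the room on the day, which the footnotes to Table 7 allow for ultrasound, cystoscopy and urodynamics. Repeat the comparison without those cases.
- Report the Table 2 time descriptively, for PUL only, and do not test it against surgery.

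The cost is a short addition to 16.6, start and stop fields on the retrospective procedure form and a flag for same-day tests. The PUL room times are already collected. There are three downsides. The PUL time will look less favourable than on the device clock. Some surgical charts will drop out. Room time may also include study-only activity in the PUL arm, such as same-day tests or video recording, which the sensitivity analysis removes only in part.

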#### 4 Introduction

Benign prostatic hyperplasia (BPH) impacts quality of life by causing lower urinary tract symptoms (LUTS). The number of U.S. men with symptomatic BPH that seek treatment options is projected to

increase from 8.1 million in 2010 to 10.3 million in 2020. Current treatment options consist of watchful waiting, medical therapy and interventional procedures. Watchful waiting is generally reserved for those with mild symptoms. Over 4 million U.S. men are on medical therapy for BPH. While symptom relief is modest with an American Urological Association Symptom Index (IPSS) improvement at 1 year of 3.5-7.5 vs. 0-5.7 for placebo, the incidence of side effects along with inadequate relief prompt over one-quarter of men on drug therapy to discontinue treatment early.

Most surgical approaches remove prostate tissue and, while highly effective, present with significant morbidity. The gold standard remains transurethral resection of the prostate (TURP) that is associated with a 14.9 point improvement in IPSS at 1 year. This improvement, however, also comes with a 20% rate of perioperative morbidity and long-term complications that include urinary incontinence (3%), urethral stricture (7%), erectile dysfunction (10%) and ejaculatory dysfunction (65%). Because tissue is removed and underlying tissue injured, there is a healing response and tissue inflammation such that subjects experience routine catheterisation and irritative symptoms post-procedure. For these reasons, the number of TURP surgeries among the US Medicare population has been declining (from 72,163 in 1999 to 49,683 in 2005). Laser vaporisation is a newer approach to TURP that minimises blood loss compared to conventional TURP, but still typically requires general or spinal anaesthesia and overnight hospital stay. There is routine catheterisation and post-operative dysuria, again as a result of tissue removal and injury. US Medicare data show that from 2005 to 2007, conventional TURP surgeries decreased by over 12,600 procedures while laser vaporisation procedures increased by over 12,100 procedures. Thus, laser vaporisation has been employed more as a

---

 Roehrborn, C.G., Current medical therapies for men with lower urinary tract symptoms and benign prostatic hyperplasia: achievements and limitations, *Rev Urol* 2008; 10:14.

Thermotherapies such as transurethral microwave therapy (TUMT), transurethral steam injection (TSI) and transurethral needle ablation (TUNA) induce necrotic scarring of the prostate as a replacement for surgical resection. The effectiveness is greater than that of drugs but less than that of TURP (10.2 and 9.1 point improvement in IPSS at 1 year for TUMT and TUNA, respectively). There is a significant shortcoming of these thermotherapies that the subject experiences within the initial months after treatment. By nature of inducing thermal injury to the prostate, there is a healing response, tissue inflammation and irritative voiding symptoms in virtually all subjects. Post-procedure, subjects face routine catheterisation, a 20-25% risk of acute urinary retention, and irritative voiding symptoms that last for 4-6 weeks. During the Prostalund Coretherm IDE study, the three TUMT patient groups experienced 14, 18, and 20 days mean post-treatment indwelling catheter time. In addition, TUMT therapies have been associated with > 20% retrograde ejaculation rate. Thus, procedure volumes for thermotherapies among Medicare beneficiaries only increased gradually to modest levels of 37,637 in 2005 and have been declining since.

With a high prevalence of subjects who discontinue medical therapy and a relatively low incidence of interventional treatment, there is a large subject population that remained inadequately addressed until the advent of the Prostatic Urethral Lift (PUL) procedure. The UroLift® System was originally approved via De Novo (DEN130023) and Special 510(k) K133281. PUL is a tissue-sparing minimally invasive treatment for BPH, is based on the hypothesis that LUTS secondary to BPH could be treated by mechanically disassociating the obstructing prostatic lobes instead of removing or injuring prostate tissue, thereby offering the ability to relieve symptoms with low morbidity and a better subject experience. At one year, subjects demonstrate an IPSS improvement similar to or better than thermotherapy (10.8 points), but the difference was the very low morbidity endured to reach that result. Catheterisation was only 32% for a mean duration less than a day. IPSS significantly improved

---

 Summary of Safety and Effectiveness, Prostalund CoreTherm Microwave Therapy System, PreMarket Approval (PMA) Number P010055.

